#### **12.2.** Efficacy evaluation

#### 12.2.1 Primary efficacy analysis

Progression free survival (PFS) is defined as the time from start of lenalidomide monotherapy to the first occurrence of disease progression or death on study from any cause, whichever occurs earlier. All treated patients will be included in efficacy endpoint analysis. Those patients who are treated on this trial but have not had a relevant event at the time of last follow-up will be included in the analyses of these endpoints as censored observations.

Page 66 of 86 Confidential

The primary endpoint is the point estimate of the 12-month PFS rate for the overall response adaptive approach. Number and percentage of patients who survived greater or equal to 365 days without disease progression will be summarized. The 95% confidence interval will be calculated using the exact binominal method. The PFS curves will be estimated by the Kaplan-Meier method. Median and its 95% confidence intervals will be estimated.

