## STUDY ENDPOINTS

#### **Primary:**

1- The 12-month progression free survival (PFS) of older adults with mildly symptomatic multiple myeloma treated on this response adapted approach (i.e. time from lenalidomide start to failure of lenalidomide and low dose dexamethasone)

Page 6 of 86 Confidential

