## **Exploratory**

- 1-Measure a lenalidomide induced tumor specific immune response and correlate the tumor specific immune response with corticosteroid use, response to therapy and duration of response
- 2- To evaluate the impact of lenalidomide mono-therapy on expression of tumor suppression genes and cell cycle regulators

STUDY DURATION: Patients will receive study therapy until evidence of disease progression on lenalidomide and low dose dexamethasone, unacceptable toxicity or withdrawal of consent

**TOTAL SAMPLE SIZE:** approximately 30 patients enrolled at Moffitt and 30 patients enrolled in a parallel identical design study in multiple sites in South Korea.

**STUDY DRUG SUPPLIES:** Lenalidomide capsules will be supplied by Celgene Corporation at no charge through the RevAssist® program.

Commercial supplies of dexamethasone (Decadron®) and prednisone tablets will be utilized.

Commercial supplies of aspirin will be utilized.

Page 7 of 86 Confidential

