## 5. Study Endpoints

## **Primary:**

1- The 12-month progression free survival (PFS) of older adults with mildly symptomatic multiple myeloma treated on this response adapted approach (i.e. time from start of lenalidomide to failure of lenalidomide and low dose dexamethasone)

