In addition, this study will evaluate the role of an alternative corticosteroid in combination with lenalidomide. Prednisone is known to be a better tolerated corticosteroid than dexamethasone without a compromise in the efficacy. This was seen in a recent report of a clinical trial by the national cancer institute of Canada study comparing melphalan prednisone to melphalan dexamethasone (grade 3 and 4 infections; 9 versus 15%, p=0.03)[18]. In addition, the intergroupe francais du myelome (IFM) had noted similar finding in older adults with newly diagnosed myeloma randomized to melphalan prednisone or dexamethasone based induction[19]. Both trials did not note a superiority of dexamethasone based induction to the prednisone based induction.

Page 26 of 86 Confidential

The primary endpoint of this study will be the progression free survival of patients treated with this response adapted approach. This is defined as the time from enrollment to failure of lenalidomide and low dose dexamethasone. Outcomes of this cohort of patients treated with this response adapted approach would be compared to patients treated with lenalidomide and low dose dexamethasone. If this response adapted approach results in similar or improved outcomes compared to therapy with lenalidomide and low dose dexamethasone, this approach would be favored since it likely result in less toxicity by using an overall lower dosage of corticosteroid.

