Page 77 of 86 Confidential Increase of ≥25% from baseline in serum M-component, and the absolute **Progressive Disease** increase must be  $\geq 0.5$  g/dl. If the starting M-component is  $\geq 5$  g/dl, increases >1 g/dl are sufficient to define relapse. • Increase of ≥25% from baseline in urine M-component, and the absolute increase must be  $\geq 200 \text{ mg/}24 \text{ hours}$ • Only in patients without measurable serum and urine M-protein levels: Increase of ≥25% from baseline in the difference between involved and uninvolved FLC levels, and the absolute difference must be >10 mg/dl Increase of ≥25% from baseline in bone marrow plasma cell percentage, and the absolute % must be  $\geq 10\%$  (relapse from CR has the 5% cutoff versus 10% for other categories of relapse) • Definite development of new bone lesions or soft tissue plasmacytomas or definite increase in the size of existing bone lesions or soft tissue plasmacytomas • Development of hypercalcemia (corrected serum calcium >11.5 mg/dl or >2.65 mmol/l) that can be attributed solely to the plasma cell proliferative V. 3 12/06/2010

- Serum M-protein  $\geq 1$  g/dl ( $\geq 10$  gm/l) [10 g/l]

disorder.

- Urine M-protein  $\geq 200 \text{ mg}/24\text{h}$ 

Serum FLC assay: Involved FLC level ≥ 100 mg/dl (≥ 100 mg/l) provided serum FLC

ratio is abnormal

Page 78 of 86 **Appendix III: ECOG Performance Status Scale** Confidential

SCORE	DESCRIPTION
0	Fully active, able to carry on all pre-disease performance
	without restriction.
1	Restricted in physically strenuous activity but ambulatory and
	able to carry out work of a light or sedentary nature, e.g., light
	housework, office work.
2	Ambulatory and capable of all self-care but unable to carry
	out any work activities. Up and about more than 50% of
	waking hours.
3	Capable of only limited self-care, confined to bed or chair
	more than 50% of waking hours.
4	Completely disabled. Cannot carry on any self-care. Totally
	confined to bed or chair.
5	Dead.

Page 79 of 86 Confidential

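### The endpoint sections define the primary 12-month PFS event as failure of lenalidomide plus low-dose dexamethasone, but 12.2.1 as worded would count the first progression or death

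*Combined protocol and SAP*

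**What the plan says.** Three places tie the primary event to the last treatment step. The Synopsis (Study Endpoints) has "time from lenalidomide start to failure of lenalidomide and low dose dexamethasone". Section 5 has "time from start of lenalidomide to failure of lenalidomide and low dose dexamethasone". Section 6.2 says: "This is defined as the time from enrollment to failure of lenalidomide and low dose dexamethasone".

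Section 12.2.1, the primary efficacy analysis, defines PFS as "time from start of lenalidomide monotherapy to the first occurrence of disease progression or death on study from any cause". For the 12-month rate it adds: "Number and percentage of patients who survived greater or equal to 365 days without disease progression will be summarized". The interval is exact binomial. Patients without an event at last follow-up are censored, and the curve is Kaplan-Meier.

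Under the Study Design part of the Synopsis and Section 6.1, progression before dexamethasone does not end study treatment. Dexamethasone is added, or may be added, and only progression on Ld takes the patient off study. The Study Duration entry agrees: "Patients will receive study therapy until evidence of disease progression on lenalidomide and low dose dexamethasone, unacceptable toxicity or withdrawal of consent".

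Section 12.1 assumes 85% for the response-adapted approach, cites about 70% for Ld, and sizes the study on the precision of the estimate with 60 patients. Section 6.2 states the intended use: "Outcomes of this cohort of patients treated with this response adapted approach would be compared to patients treated with lenalidomide and low dose dexamethasone".

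**The concern.** The two definitions answer different questions. One asks whether the whole strategy has failed by 12 months, the other whether the first progression has occurred. They part on the very path that the design creates: progression on lenalidomide or lenalidomide-prednisone, followed by control on Ld.

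There is no hypothesis test, so the estimate and its interval are the primary result. Section 6.2 says that similar or better outcomes than Ld would favour this approach. Which rate is set beside the 70% therefore matters to the reading of the trial. While the text is unreconciled, the choice could be made with the data in view.

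**Working it through.** **1. The plan's own figure.** Inputs from 12.1 and 12.2.1: n = 60, assumed rate 85% (x = 0.85 × 60 = 51), exact binomial method. The Clopper-Pearson limits are the 2.5% quantile of Beta(x, n − x + 1) and the 97.5% quantile of Beta(x + 1, n − x). For 51/60 they are 73.4% and 92.9%, as stated in 12.1. The arithmetic is sound for whichever event the 85% means.

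**2. The same patient under both texts, at day 365.**

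| Course to day 365 | Endpoint sections (Ld failure) | 12.2.1 as worded |
|---|---|---|
| Alive, never progressed | Event-free | Event-free |
| Progressed before dexamethasone, added it, no progression on Ld | Event-free | Event |
| Progressed on Ld | Event | Event |
| Progressed, never started dexamethasone | Not stated | Event |
| Stopped Ld without progression on it | Not stated | Event already counted |
| Stopped or lost before day 365, never progressed | Not stated for the 365-day count | Not stated for the 365-day count; censored for Kaplan-Meier |

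The second row is the conflict. In the design as described, dexamethasone is given only after a progression. Under the literal 12.2.1 rule, every patient who reaches Ld is therefore already an event, and what happens on Ld cannot change the primary rate.

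**3. Size.** Let k be the number of patients in the second row. Taking failure as progression on Ld or death, with deaths counted alike and the unstated rows set aside, the 12.2.1 rate is the strategy rate minus k/60. One patient moves it by 1/60 = 1.7 points. The documents do not give k, so the values below are assumptions, with 51/60 taken as the strategy result.

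| Assumed k | 12.2.1 count | Rate | Exact 95% interval |
|---|---|---|---|
| 0 | 51/60 | 85.0% | 73.4-92.9% |
| 1 | 50/60 | 83.3% | 71.5-91.7% |
| 3 | 48/60 | 80.0% | 67.7-89.2% |
| 6 | 45/60 | 75.0% | 62.1-85.3% |

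A patient who stops Ld without progression moves the strategy rate by the same 1.7 points, depending on whether the stop counts as failure.

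**4. Time origin.** Section 6.2 starts the clock at enrollment. The Synopsis, Section 5 and 12.2.1 start it at lenalidomide.

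**5. Timing.** Moffitt enrolled from 2/2010 to 6/2013 (Rationale for Amendment 6). Twelve months after the last enrollment is about mid-2014, before Version 6 of 4/15/2016.

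**The case against.** The best defence is that 12.2.1 is a generic PFS sentence loosely reused. Both 12.1 and 12.2.1 speak of the overall response-adapted approach, which the Synopsis and Section 5 spell out as time to Ld failure. PFS on single-agent lenalidomide is a separate secondary endpoint with its own curve in 12.2.2, and that curve would largely duplicate the primary under the literal rule. Section 12.2.5 ends duration of response at progression on lenalidomide and dexamethasone. This stands as evidence of intent, and it is why the point is put as what 12.2.1 as worded would compute. It does not settle the matter: naming the strategy does not alter a first-occurrence rule or the literal 365-day count.

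Four stronger readings are tempting but not supported.

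- That failure is wholly undefined. The Study Design and Study Duration entries and 12.2.5 together point to progression on Ld, and 12.2.1 already censors event-free patients in the Kaplan-Meier analysis. What remains open is the 365-day count and the unstated rows above.
- That Appendix II, with "Increase of ≥25% from baseline in serum M-component", makes a patient who progressed earlier count as progressing on Ld from its first day. That would make the dexamethasone step pointless, and the schedule calls for reassessment when a corticosteroid is added. It is fair to say only that no passage names the reference value.
- That the 12.2.1 wording would pull the result down to the 70% reference. That needs nine of 60 patients in the second row (42/60), and nothing in the documents supports that number.
- That the 70% holds under either definition. This depends on how the reference studies defined PFS, which 12.1 does not say.

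On direction, the literal 12.2.1 rule gives the lower rate and cannot flatter the strategy. Adopting the strategy event now adopts the more favourable figure after the Moffitt windows closed. That objection stands and shapes the fix.

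**Conclusion.** The conflict is real and should be resolved before the primary result is reported. Three places define the primary event as Ld failure, 12.2.1 as worded counts first progression or death, and no text reconciles them or says which event the 85% describes. The difference is 1.7 points of 60 for each patient who progresses before dexamethasone and is then controlled to day 365. Any total shift, such as 85.0% to 80.0% with three patients, is an assumption. The direction rests on reading failure as progression on Ld or death; a rule that counted other stops of Ld as failure could narrow or reverse it.

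A reader might infer that an error rate is affected or that the stated interval is wrong. Neither follows: the plan has no test, and the interval reproduces. The harm is to the meaning of the primary estimate and to the comparison with Ld in 6.2.

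**What to change.** - Reconcile the Synopsis, Section 5, Section 6.2 and 12.2.1 to one primary event and one time origin, the first lenalidomide dose.
- If the sponsor confirms the strategy endpoint, define the event in 12.2.1 as progression on Ld or death from any cause. State how to count patients who progress and never start dexamethasone, those who stop Ld without progression, and those censored before day 365. Apply the same event and rules to the 365-day count.
- State in 12.1 which event the 85% uses.
- Report time to first progression or death as a named endpoint. Show both rates with equal prominence wherever the result is set beside the 70%, and state as an assumption how the reference studies defined PFS.
- Reconcile the Study Design and Study Duration entries with Appendix II on what counts as progression on Ld after an earlier progression. This criterion also takes patients off study, so it is for the sponsor to settle; no reference value is proposed here.
- Apply the same definition to the South Korean cohort before pooling, after checking that dates of first progression, dexamethasone start and later progression were recorded there.
- Date the clarification. Disclose that it was made after the Moffitt 12-month windows had closed, and that the strategy event so defined gives a rate equal to or higher than the present 12.2.1 wording.

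The cost is wording, the date check, one more Kaplan-Meier analysis, and a less favourable figure shown alongside the primary one.

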#### STUDY DESIGN:

This is a multi-center, single-arm, phase 2, open-label study of lenalidomide [Revlimid® (R)] based therapy in older adults with standard risk multiple myeloma. After enrollment patients will receive single agent lenalidomide. Responders (minimal response or better) after 2 cycles will continue present therapy until disease progression or intolerable toxicity. Patients with stable disease after 2 cycles will receive prednisone (100 mg orally on days 1 to 5 of each cycles) in addition to lenalidomide. Patients with evidence of disease progression after 2 cycles of single agent lenalidomide will receive low dose dexamethasone (40 mg weekly) in addition to lenalidomide. Patients not receiving low dose dexamethasone and with disease progression at any time during the study will be eligible to receive low dose dexamethasone in combination with lenalidomide. Patients on lenalidomide and low dose dexamethasone who experience disease progression at any time during the study will be taken off study and treated with alternative therapies..

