## 6. Investigational Plan

## 6.1. Overall design

This is a phase 2 trial evaluating a lenalidomide based response adapted strategy in older adults with newly diagnosed multiple myeloma. Subjects will be started on single agent lenalidomide. In the event of disease progression, low dose dexamethasone will be added (see diagram below). In the event of stable disease after 2 cycles of therapy, the use of an alternate corticosteroid (prednisone) will be added to lenalidomide therapy (see diagram below). In the event of a minimal response after 2 cycles of single agent lenalidomide therapy, such therapy will be continued until disease progression (see diagram below).

Page 24 of 86 Confidential

Subject replacement and evaluable patients

Subjects who discontinue study drug, other then for progression, prior to completing one cycle of therapy will be replaced.

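### The primary PFS event is failure of lenalidomide plus low dose dexamethasone in sections 1, 5 and 6.2, but first progression or death in section 12.2.1

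*Combined protocol and SAP*

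**What the plan says.** The synopsis (section 1) gives the primary endpoint as 12-month PFS, explained as "time from lenalidomide start to failure of lenalidomide and low dose dexamethasone". Section 5 has "time from start of lenalidomide to failure of lenalidomide and low dose dexamethasone". Section 6.2 says of the primary PFS: "This is defined as the time from enrollment to failure of lenalidomide and low dose dexamethasone". The three agree on the event; section 6.2 differs in starting the clock at enrollment.

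Section 12.2.1 runs PFS from the start of lenalidomide monotherapy to "the first occurrence of disease progression or death on study from any cause, whichever occurs earlier". It then states: "The primary endpoint is the point estimate of the 12-month PFS rate for the overall response adaptive approach". The rate is the proportion of patients alive and progression-free at day 365, with an exact binomial interval.

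The treatment plan makes progression before Ld a step within the strategy. From the synopsis: "Patients with evidence of disease progression after 2 cycles of single agent lenalidomide will receive low dose dexamethasone". Patients not yet on dexamethasone who progress at any other time "will be eligible to receive low dose dexamethasone in combination with lenalidomide". Section 6.1 is firmer: "In the event of disease progression, low dose dexamethasone will be added". Only progression on Ld takes a patient off study.

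Section 12.1 expects a 12-month PFS of 85% for the adaptive approach and cites about 70% for Ld. It does not say which event the 85% refers to.

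**The concern.** Under the protocol Ld is added only at progression, because stable disease after two cycles leads to prednisone instead. Every patient who starts Ld as planned has therefore already had a section 12.2.1 event before the first Ld dose. The primary rate becomes a measure of lenalidomide with or without prednisone, and the Ld step drops out.

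Section 6.2 states a different aim: to set the outcome of the whole adaptive approach against treatment with Ld. A rate that treats the planned rescue as failure does not answer that question. An analyst who follows section 12.2.1 and one who follows section 5 could report different primary results from the same data, and both could cite the protocol.

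**Working it through.** **1. Where the definitions part at day 365**

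| Course | Section 12.2.1 | Ld-failure wording |
|---|---|---|
| Alive, no progression by day 365 | free | free |
| First progression after day 365 | free | free |
| Progression before Ld and Ld failure, both by day 365 | event | event |
| Progression before Ld by day 365, then on Ld, alive without Ld failure at day 365 | event | free |
| Progression by day 365, never starts Ld, alive at day 365 | event | no event named |
| Death by day 365 without progression | event | not named, but implied by the term PFS |

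The binary rate differs for the fourth row and, on a literal reading, the fifth. In the Kaplan-Meier curve the event time differs for everyone who progresses before Ld.

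**2. The plan's own figure**

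Inputs from sections 12.1 and 12.2.1: n = 60, expected rate 85%, exact binomial 95% interval.

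- x = 0.85 × 60 = 51.
- Clopper-Pearson limits are the 2.5% quantile of Beta(x, n−x+1) and the 97.5% quantile of Beta(x+1, n−x).
- For 51/60: Beta(51, 10) gives 73.4% and Beta(52, 9) gives 92.9%.

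This reproduces the stated 73.4-92.9%. The arithmetic is sound; what is unsettled is the event it describes.

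**3. Effect per patient**

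1/60 = 1.67 percentage points for each patient classified differently.

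**4. Sensitivity**

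Let k be the number of patients who progress before Ld by day 365 and are alive without Ld failure at day 365. The documents do not give k, so the values below are assumptions. Suppose that 85% is the Ld-failure rate. The section 12.2.1 rate is then (51 − k)/60:

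| k | Rate under 12.2.1 | Exact 95% CI |
|---|---|---|
| 0 | 51/60 = 85.0% | 73.4-92.9 |
| 3 | 48/60 = 80.0% | 67.7-89.2 |
| 6 | 45/60 = 75.0% | 62.1-85.3 |
| 9 | 42/60 = 70.0% | 56.8-81.2 |

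If 85% was instead meant as first-progression PFS, the shift runs the other way: the Ld-failure rate is (51 + k)/60, for example 54/60 = 90.0% at k = 3.

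**The case against.** The strongest reply is that the intent is easy to identify. Three sections name Ld failure. Sections 12.1 and 12.2.1 both attach the rate to the overall adaptive approach. PFS on single agent lenalidomide is a separate secondary endpoint, which a first-progression primary would largely duplicate. On this view section 12.2.1 contains a drafting slip, and the trial only estimates a rate, with no test or threshold.

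Much of this stands. It is a good reason to resolve the conflict in favour of Ld failure. But it does not remove the conflict: section 12.2.1 is the operative analysis text, its first-occurrence rule is explicit, and naming the strategy does not change the event. No section says which definition governs.

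Some stronger readings are tempting but not supported:

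- A reader might infer that every patient who progresses before Ld is classified differently. That holds for event time in the Kaplan-Meier curve. It is false for the 12-month rate, as the second and third rows of the table show.
- A reader might size the gap from the single-agent study in section 4.2.2. That study was in relapsed or refractory disease and reports response categories, not 12-month progression. It does not say which response categories the 30 patients given dexamethasone came from. It cannot bound k here.
- A reader might infer that the Ld-failure wording counts patients who progress and never start Ld as successes. The wording is silent on them, and no section states such a counting rule. Nor do the documents say how often this would happen. The silence is still a gap, since later progressors are only eligible for Ld and section 8.1.7 allows study drug to stop at progression.
- A reader might suspect that the definition would be picked to suit the results. Nothing in the documents shows this; the wording merely leaves room for it.

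**Conclusion.** The contradiction is in the current text and is unreconciled. Followed as written, section 12.2.1 counts planned escalation to Ld as failure, so the primary rate cannot reflect the Ld step that the strategy includes.

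The firm part of the size is 1.67 points per affected patient at n=60. The total is unknown because the plan does not give the number affected. The 80.0%, 75.0% and 70.0% results rest on assumed counts of 3, 6 and 9, and on assigning the 85% to Ld failure. Reaching 70.0% would match the Ld figure in section 12.1, but that figure is an informal reference and not a decision threshold, so no count of reclassified patients makes the trial fail.

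**What to change.** In section 12.2.1, replace the event with:

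> The earliest of progression on Ld, death from any cause, or progression on lenalidomide or lenalidomide-prednisone in a patient who never receives Ld on study (dated at that progression).

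Use the same wording in sections 1, 5 and 6.2, with the start of lenalidomide as the time origin throughout. State in section 12.1 which event the 85% refers to. Report first-progression PFS alongside as a secondary result, with the number of patients who progressed and never received Ld.

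Do not add a fixed window, such as 28 days, for starting Ld. Section 8.1.6 holds a new cycle until toxicity resolves and foresees delays beyond 4 weeks, so a fixed limit could fail a patient who then starts Ld as planned.

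Costs:

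- It is a late clarification of the primary event. Moffitt enrolled its last patient in 6/2013, so its 12-month data had matured by about 6/2014, and the current version is dated 4/15/2016. The report should say that the change came after that point. Giving both rates limits the concern.
- Some chart review is needed for patients who left study drug, because off-study follow-up is for survival (section 2) and recording of therapies ends at the last dose (section 9.5).
- The parallel South Korean study supplies 30 of the 60 patients and needs the same change.
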